6.1 Study Flow

The study will implant up to 535 subjects. Assuming a dropout rate of approximately 10% by 6 months, this study will implant a maximum of 450 patients in Cohort #2 and Cohort #3. This is to achieve at least 406 implanted patients with complete follow-up at 6 months. After completion of enrollment and as soon all 406 subjects reach their 6 month follow- up visit, the 6 month primary endpoint data will be used for Premarket Approval (PMA) submission. Up to 85 subjects (cross- over from former **Control Arm**) will continued to be followed in Cohort #1.

[figure not shown]

Figure 9: Study Flow

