This document is confidential.

study success. Analysis will be based on a Poisson regression approach for the number of events, with the log follow-up time as an offset term. Sensitivity analyses using a negative binomial approach to capture within-subject correlation will be performed.

The study will implant 450 subjects (combined in Cohort#2 and Cohort#3) leading to an expected evaluable cohort of 406 subjects. With a goal of 0.43 and a one-sided 0.025 alpha level, the study will have greater than 80% power assuming a population treatment rate of 0.34. Calculations are based on a one-sample Poisson rate test and were performed with PASS 2021.

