7.1.1. Main analysis

The mathematical statement of the null and alternative hypothesis is as follows:

$$H_0: r_6 \geq PG_6$$

$$H_A: r_6 < PG_6$$

will be used for the goal. The null hypothesis will be rejected if the upper confidence bound for the rate is less than the performance goal, or equivalently, that the corresponding p-value from the hypothesis test is less than 0.025. An observed rate of less than 0.37 and rejection of the null hypothesis indicate that the observed rate is statistically less than the performance goal, indicating clinically acceptable results and study success. Analysis will be based on a Poisson regression approach for the number of events, with the exposure time as an offset term, where r_6 is the 6-month rate of primary endpoint events and PG_6 is the performance goal. A value of 0.43 will be used for the goal.

The test will be based on each subject's total number of events, treatment arm, and exposure time, where a subject's exposure is the time to death, early study discontinuation or 6 months, whichever is smaller.

```
proc genmod data = xxx;  
    model number of events = dummy /*(dummy variable)*/ / noint type3 dist=poisson  
offset=log(exposure_time);  
run;
```

All events until day x, which would be exact 6 months (180 days) post-implant visit would be summarized by cohort. The estimated 6 month incidence of HF related hospitalizations (HFH) or all-cause mortality, along with the 2-sided 95% CIs for the estimated will be presented, and p-value from the hypothesis test. The presentation will also include number of HFH, all-cause mortality, total number of both events, and subjects' event rate of HFH or all-cause mortality is calculated as the total number of observed events per subject divided by the (subject's observed exposure time/180) from implant through 6 months, where a subject's exposure is the time to death, early study discontinuation or 6 months (180 days) post implant visit, whichever is the smallest.

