All events until day x, which would be exact 6 or 12 months (180 or 365 days respective) post-implant visit would be summarized.

All events happened between day x and implant visit, which is exact 6 or 12 months (-180 or -365 days respective) pre-implant visit. Analysis will be done based on mITT population, PP population, and Cohort #1 population. Prior to the date of cut-off for the main analysis, it will be confirmed, if analysis based on PP population will be required.

This document is confidential.

7.1.6. Comparison of the number of HF Hospitalizations or Emergency Department/ Hospital Outpatient IV diuretic visits of Cohort #1 and Cohort #2 + Cohort #3 at 6 and 12 month post implant

The rate of mortality and HF hospitalizations or HF emergency department/hospital outpatient IV diuretic visits in each cohort at 6 or 12 month is calculated as the total number of observed events in each cohort divided by the (total observed exposure time/180 or 365) in each cohort from implant visit through 6 months or 12 months.

The information on mortality will be used as collected on the CRF, AE page with AE outcome = 'Death' or Study completion page with primary reason for discontinuation = 'Death'. The information on HF hospitalizations will be used as collected on the CRF, Hospitalization page, emergency department/hospital outpatient IV diuretic visits will be used as collected on the CRF, AE page with AEs resulted in = 'Emergency Department (ED) visit'/'Hospitalization'/'Urgent, unscheduled outpatient office/ practice' for AE categorized as 'Heart failure'.

The Cohort #1 and Cohort #2 + Cohort #3 subjects will then be compared with respect to rate of events per unit time using poisson regression. The test will be based on each subject's total number of events, treatment arm, and exposure time, where a subject's exposure is the time to death, early study discontinuation or 6 or 12 months, whichever is smaller.

Let λ_1 be the rate of events per 6/12 month on the Cohort #1 and let λ_2 be the rate of events per 6/12 month on the Cohort #2 + Cohort #3. The null hypothesis is $H_0: \lambda_1 \leq \lambda_2$ and the alternative hypothesis is $H_1: \lambda_1 > \lambda_2$.

The poisson regression calculation provides a one-sided p-value for the null hypothesis that the rate in the Cohort #1 is less than or equal to the rate in the Cohort #2 + Cohort #3.. The resulting p-values will be seen as explanatory.

```
proc genmod data = xxx;  
    class trt;  

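### SAP 7.1.1 puts a per-subject event rate that early deaths inflate into the primary efficacy presentation, and never names the rate to which the 0.37 success condition applies

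*SAP*

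**What the plan says.** SAP 7.1.1 sets two conditions for success: "An observed rate of less than 0.37 and rejection of the null hypothesis". On the performance goal it says "A value of 0.43 will be used for the goal". The test is a Poisson model with log exposure as offset. The section asks for the estimated 6-month incidence with its 95% interval and p-value.

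The same paragraph then lists further items for the presentation. The last is the subjects' event rate. This "event rate of HFH or all-cause mortality is calculated as the total number of observed events per subject", divided by that subject's observed exposure over 180. The subject's "exposure is the time to death, early study discontinuation or 6 months (180 days) post implant visit, whichever is the smallest". The section does not say how these ratios are to be summarised. The default in SAP 5.1 for a continuous variable is n, mean, SD, median, minimum and maximum.

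For the cohort comparison, SAP 7.1.6 uses a different form. There the rate "is calculated as the total number of observed events in each cohort divided by the (total observed exposure time/180 or 365"), that is, pooled events over pooled exposure.

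SAP 2.4.1 and Protocol 10.3 state the success rule as an upper confidence bound of the observed event rate below 0.43, together with an observed event rate below 0.37. Neither gives a formula for this trial's observed rate.

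**The concern.** In this endpoint death is both an event and the end of exposure. A subject who dies on day t with no hospitalization contributes 1/(t/180) = 180/t to the set of ratios. A death on day 5 counts as 36. The unweighted mean gives that subject the same weight as one followed for 180 days, so a few early deaths can dominate it.

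Two things are at stake. First, the primary table would carry a rate well above the Poisson estimate printed beside it, although both claim to describe 6-month events. Second, one of the two success conditions depends on an observed rate that is not identified. In 7.1.1 only the per-subject ratio is described in terms of observed events and observed exposure. The Poisson result is called estimated.

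**Working it through.** **Inputs.** SAP 2.4.1: "one-sided 0.025 alpha level, the study will have greater than 80% power assuming a population treatment rate of 0.34", and 450 implants "leading to an expected evaluable cohort of 406 subjects". Protocol 6.1: "Assuming a dropout rate of approximately 10% by 6 months". Goal 0.43 and cap 0.37 come from SAP 7.1.1. Six-month mortality comes from the prior-study table in SAP 2.4.1: 15/270 = 5.6%, 107/1200 = 8.9% and 16/234 = 6.8%. GUIDE-HF has 0.089 at 12 months, and 1 − √(1 − 0.089) = 4.6%, or about 4.5% by halving.

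**1. The plan's own figure.** Exact one-sample Poisson test with n = 406: the largest c with P(X ≤ c | 406 × 0.43) ≤ 0.025 is c = 148, a rate of 148/406 = 0.3645. Power is P(X ≤ 148 | 406 × 0.34) = 81.4%. The stated power above 80% is reproduced.

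**2. The two conditions on the pooled rate.** At n = 406, 0.37 × 406 = 150.2, so the cap allows 150 events and the confidence bound allows 148. At n = 450, 0.37 × 450 = 166.5, and both allow 166. On the pooled rate the cap takes no power from the design.

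**3. Poisson estimate and pooled rate.** With a single constant term and offset log(exposure), the fitted rate is total events / total exposure. Multiplied by 180, it is the pooled 6-month rate.

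**4. What a death does to the mean ratio.** Averaged over death days 1 to 180, 180/t is 1 + 1/2 + … + 1/180 = 5.77, where the pooled numerator counts 1. One death with a single day of exposure adds 180/450 = 0.40 to the mean, which exceeds 0.37 by itself.

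**5. Worked example.** 450 subjects, 25 deaths evenly spread over 180 days, and 124 hospitalizations, all in survivors.
- Events: 25 + 124 = 149. Exposure: 425 + 25 × 0.5 = 437.5 periods of 180 days.
- Pooled rate: 149/437.5 = 0.341. Upper bound: 0.341 × exp(1.96/√149) = 0.400. Both conditions are met.
- Sum of 180/t over the 25 deaths: 129.6. Mean ratio: (124 + 129.6)/450 = 0.563. This is above 0.37.

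**6. Simulation.** 4,000 trials per row, 450 subjects, true pooled rate 0.34 per 180 days, 10% dropout by 6 months. Assumptions: constant hazards, death independent of hospitalization, exposure rounded up to whole days. The last column is the share of trials meeting both conditions on the pooled rate whose mean ratio is 0.37 or more.

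| 6-month mortality | Mean pooled rate | Mean of per-subject ratios | Otherwise successful trials failing 0.37 |
|---|---|---|---|
| 0% | 0.34 | 0.34 | 5% |
| 1% | 0.34 | 0.39 | 38% |
| 3% | 0.34 | 0.48 | 81% |
| 4.5% | 0.34 | 0.55 | 93% |
| 6% | 0.34 | 0.63 | 98% |
| 8.9% | 0.34 | 0.77 | 99.8% |

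Both conditions are met on the pooled rate in 82% to 84% of trials in every row. Without dropout the mean ratios are nearly the same (0.39, 0.49, 0.56 and 0.78 at 1%, 3%, 4.5% and 8.9%).

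**The case against.** The strongest reply is that nothing in the plan applies the per-subject ratio to the 0.37 condition. SAP 7.1.1 specifies the Poisson model, prints its code and asks for its estimate with an interval, and that estimate is the pooled rate. SAP 2.4.1 and Protocol 10.3 use one term for both conditions. An upper confidence bound is planned only for the Poisson rate, so the observed event rate there most naturally means that estimate. The ratio is introduced as something the presentation also includes, and no instruction says to average it. The 0.37 threshold was itself built from events over numbers of subjects at study level. SAP 7.1.6 defines a cohort rate for a different endpoint, so it does not strictly contradict a subject-level display.

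Most of this stands. A reader might infer that the SAP's success rule would fail a device that meets it, or that the per-subject ratio is the only rate the SAP defines for the primary endpoint. The documents support neither. The failure percentages above describe a possible misreading; they are not the planned rule.

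Two things remain. Section 7.1.1 never says that 0.37 applies to the Poisson estimate, so a success criterion rests on inference. And the ratio, summarised as SAP 5.1 prescribes, is not a usable description of the 6-month rate. Its mean is inflated, and its median would be about 0, because at a rate of 0.34 roughly exp(−0.34) = 71% of subjects have no event.

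**Conclusion.** The point holds as a defect in a reported statistic and a gap in the wording of the success rule. It is not an error in the hypothesis test. At the mortality implied by the plan's own prior-study tables (about 4.5% to 8.9%), the mean per-subject rate would be about 0.55 to 0.77 when the true pooled rate is 0.34. The inflation depends on mortality: it is small at 1% (0.39) and absent with no deaths. The simulated figures rest on constant hazards, independence of death and hospitalization, and 10% dropout. The first two are assumptions not found in the documents. Step 4 needs none of them.

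The likelier consequence is a primary table with two discordant rates. The graver one, a false failure on 0.37, needs a reading that the documents do not favour, but which one sentence would exclude.

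**What to change.** In SAP 7.1.1, replace the per-subject formula with total events divided by (total exposure/180), the form used in 7.1.6. State that the 0.37 condition applies to this pooled rate, which is the Poisson point estimate on the 180-day scale. The printed code uses log(exposure_time), so with exposure in days its coefficient is a log daily rate. Either use the offset log(exposure_time/180) or state the multiplication by 180.

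Make the same change, with 365 days, for the 12-month endpoint and its 0.59 condition (7.1.4), and carry it through to the analyses that refer to 7.1.1: the separate hospitalization and mortality analyses in 7.1.3, and 7.1.8, 7.1.9 and 7.1.12. The separate mortality table is the most exposed: at 6% mortality with deaths evenly spread, the mean ratio would be about 0.06 × 5.77 = 0.35.

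The cost is a sentence or two in the SAP and a small programming change. No new data are needed, the hypothesis test is unchanged, and by step 2 the cap costs no power when applied to the pooled rate.

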7.1.2. Sensitivity analysis

Sensitivity analyses using a negative binomial approach (with the same terms as the poisson model used in the main analysis) to capture within-subject correlation will be performed.

This document is confidential.

7.1.3. Supplementary analysis

Then main analysis will be repeated based on the PP population and Cohort #1 population. Interpretation of the p-values will be done in descriptive manner only.

In addition, HFH and all-cause mortality from CEC adjudication results will be analysed separately using same method as the main analysis in Section [7.1.1](#). Secondary Efficacy Endpoints and Analyses

7.1.4. Incidence of HF Hospitalizations or all-cause mortality at 12 months

The mathematical statement of the null and alternative hypothesis for the first secondary efficacy is as follows:

$$H_0: r_{12} \geq PG_{12}$$

$$H_A: r_{12} < PG_{12}$$

where r_{12} is the 12 month rate of secondary endpoint events and PG_{12} is the performance goal. A value of 0.70 will be used for the goal. The null hypothesis will be rejected if the upper confidence bound for the rate is less than the performance goal, or equivalently, that the corresponding p-value from the hypothesis test is less than 0.025. An observed value of less than 0.59 and rejection of the null will indicate that the observed rate is statistically less than the performance goal, indicating clinically acceptable results.

Analysis will be based on a Poisson regression approach for the number of events, with the log follow-up time as an offset term. Sensitivity analyses using a negative binomial approach to capture within-subject correlation will be performed.

12 month incidence of HF related hospitalizations (HFH) or all-cause mortality will be analyzed on the mITT, PP and Cohort #1 population in a similar manner to the primary efficacy endpoint.

7.1.5. Number of HF Hospitalizations at 6 and 12 months post-implant compared to the number of HF Hospitalizations in the 6 and 12 months prior to implant

Heart Failure hospitalizations will be summarized by cohort presenting number of subjects without any hospitalizations at 6 and 12 months post-implant visit, number of subjects with any hospitalizations at 6 and 12 months post-implant visit, number of hospitalizations per subject at 6 and 12 months post-implant visit, and mean number of hospitalizations per subjects at 6 and 12 months post-implant visit. Similar presentation will be done based on the CRF information on the number of hospitalizations in the 6 and 12 months prior to implant. 95 % Clopper-Pearson confidence interval (CI) will be provided in addition for the frequencies as applicable. In additional, Wilcoxon rank sum tests will be performed to compare the number of hospitalizations per subject at 12 months post-implant visit with 12 months prior-implant visit, and compare the number of hospitalizations per subject at 6 months post-implant visit with 6 months prior-implant visit.

The 6 and 12 months timepoint is independently of visit information and is calculated as:

All events until day x, which would be exact 6 or 12 months (180 or 365 days respective) post-implant visit would be summarized.

All events happened between day x and implant visit, which is exact 6 or 12 months (-180 or -365 days respective) pre-implant visit. Analysis will be done based on mITT population, PP population, and Cohort #1 population. Prior to the date of cut-off for the main analysis, it will be confirmed, if analysis based on PP population will be required.

This document is confidential.

7.1.6. Comparison of the number of HF Hospitalizations or Emergency Department/ Hospital Outpatient IV diuretic visits of Cohort #1 and Cohort #2 + Cohort #3 at 6 and 12 month post implant

The rate of mortality and HF hospitalizations or HF emergency department/hospital outpatient IV diuretic visits in each cohort at 6 or 12 month is calculated as the total number of observed events in each cohort divided by the (total observed exposure time/180 or 365) in each cohort from implant visit through 6 months or 12 months.

The information on mortality will be used as collected on the CRF, AE page with AE outcome = 'Death' or Study completion page with primary reason for discontinuation = 'Death'. The information on HF hospitalizations will be used as collected on the CRF, Hospitalization page, emergency department/hospital outpatient IV diuretic visits will be used as collected on the CRF, AE page with AEs resulted in = 'Emergency Department (ED) visit'/'Hospitalization'/'Urgent, unscheduled outpatient office/ practice' for AE categorized as 'Heart failure'.

The Cohort #1 and Cohort #2 + Cohort #3 subjects will then be compared with respect to rate of events per unit time using poisson regression. The test will be based on each subject's total number of events, treatment arm, and exposure time, where a subject's exposure is the time to death, early study discontinuation or 6 or 12 months, whichever is smaller.

Let λ_1 be the rate of events per 6/12 month on the Cohort #1 and let λ_2 be the rate of events per 6/12 month on the Cohort #2 + Cohort #3. The null hypothesis is $H_0: \lambda_1 \leq \lambda_2$ and the alternative hypothesis is $H_1: \lambda_1 > \lambda_2$.

The poisson regression calculation provides a one-sided p-value for the null hypothesis that the rate in the Cohort #1 is less than or equal to the rate in the Cohort #2 + Cohort #3.. The resulting p-values will be seen as explanatory.

```
proc genmod data = xxx;  
    class trt;  
    model number of events = trt/ type3 dist= poisson offset=log(exposure_time);  
run;
```

Analysis will be done based on the Comparison population.

